4.6 MISSING DATA

Incomplete dates for AEs and laboratory data will be handled as described in the Roche data analysis standards (GDSR). Missing values will not be imputed unless otherwise specified (e.g. for BLQs).

4.7 SAFETY ANALYSES

Safety information will be collected, reviewed, and evaluated by the Sponsor or designee in accordance with the Safety Management Plan throughout the conduct of the clinical trial. Data will be summarized using descriptive statistics. Only scheduled visits will be presented in summary tables and both scheduled and unscheduled visits will be included in listings.

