4.3 STUDY TREATMENT AND OTHER TREATMENTS RELEVANT TO THE STUDY DESIGN

The investigational medicinal product (IMP) for this study is RO7234292.

Patients will receive two IT doses of the same dose strength of RO7234292 at an interval of 28 days during the treatment period (Day 1 and Day 29). Each dose of RO7234292 will be administered as a single IT bolus injection.

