5.1.3.3 Management Guidelines

Guidelines for management of specific adverse events are outlined in [Table 1](#). Additional guidelines are provided in the subsections below.

Initial clinical laboratory tests with results meeting criteria for withholding study drug must be repeated on new specimens as soon as possible, and results must be available prior to administering the next dose of study drug. In general, patients who do not reach the stopping rule may continue dosing; however, the Investigator and Sponsor should confer as to whether additional close monitoring of the patient is indicated.

Table 1 Guidelines for Management of Patients Who Experience Adverse Events

Event	Action to Be Taken

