Thrombocytopenia	
 • If platelet count is $\leq 100,000/\text{mm}^3$: 
 Monitor platelet count weekly. • If platelet count is $\leq 75,000/\text{mm}^3$ and $> 50,000/\text{mm}^3$ in the absence of major bleeding or clinically relevant non-major bleeding: 
 Withhold study drug until the platelet count has recovered to $> 100,000/\text{mm}^3$. The suitability of the patient for continued dosing and frequency of monitoring should be discussed with the Medical Monitor. • If platelet count is $\leq 50,000/\text{mm}^3$: 
 Permanently discontinue. Monitor platelet counts daily until two successive values show improvement. Then monitor every 2 to 3 days until platelet count is stable, and at least weekly until platelet count returns to normal. Administration of steroids may be considered for patients whose platelet count is $< 25,000/\text{mm}^3$.
Decreased renal function	
 • Withhold study drug in the event of a persistent (> 2 weeks) decrease of eGFR or CrCl or increase in creatinine, as defined below: 
 1. eGFR or CrCl $< 60 \text{ mL/min}/1.73 \text{ m}^2$. 2. Creatinine level increase of $2.0 \times$ above baseline. • Study Drug may be resumed when follow-up test results show that the patient no longer meets the dose interruption criteria.

ALT=alanine aminotransferase; AST=aspartate aminotransferase; CrCl=creatinine clearance; CSF=cerebrospinal fluid; eGFR=estimated glomerular filtration rate; INR=international normalized ratio; ULN=upper limit of normal; WBC=white blood cell.

Table 1 Guidelines for Management of Patients Who Experience Adverse Events (cont.)

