Elevated liver enzymes	
 ALT or AST is $> 3 \times$ ULN: 
 Monitor weekly until ALT and AST return to $\leq 1.2 \times$ ULN. Further investigation into the liver enzyme elevations may include hepatitis serologies and other diagnostic tests at the discretion of the Investigator in consultation with the Medical Monitor. Withhold study drug in the event of liver enzymes that meet the following criteria without an alternative explanation (as discussed with the Medical Monitor): 
 ALT or AST $> 5 \times$ ULN. ALT or AST $> 3 \times$ ULN, combined with total bilirubin $> 2 \times$ ULN or INR > 1.5. ALT or AST $> 3 \times$ ULN coinciding with new appearance of fatigue, nausea, vomiting, right upper quadrant pain or tenderness, fever, rash, and or concomitant eosinophilia. Discontinue study drug permanently if levels do not return to baseline after 30 days.
------------------------	--

ALT=alanine aminotransferase; AST=aspartate aminotransferase; CrCl=creatinine clearance; CSF=cerebrospinal fluid; eGFR=estimated glomerular filtration rate; INR=international normalized ratio; ULN=upper limit of normal; WBC=white blood cell.

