2. STUDY DESIGN

Eligible subjects will receive dose assigned to the cohort they are allocated to. Three dose levels are tentatively planned as follows:

- Dose level 1: 120 mg RO7234292 (n=4 patients)
- Dose level 2: 60 mg RO7234292 (n=4 patients)
- Dose level 3: 30 mg RO7234292 (n=4 patients)

This is not a randomization study. Patients are allocated to a cohort and hereby dose level according to the way they are sequentially enrolled into the study. Thus, the first 4 subjects will be assigned to 120mg, the next 4 subjects to 60mg and the next 4 subjects to 90mg.

After a review of medical data from the initial 3 dose levels and initial set of patients, a decision will be made whether to enroll additional patients and, in this case, whether to repeat a dose level, or to evaluate a lower or intermediate dose levels. The final number of dose levels and total number of patients assigned to a given dose level will be defined during the study. Up to a maximum of 20 patients will be enrolled in the whole study and the highest tested RO7234292 dose in this study will not exceed 120 mg, which is the highest test dose in the previous Phase I/IIa clinical study (ISIS 443139-CS1).

Study day is calculated relative to the date of first dose administration in Study BP40410. Study Day 1 will be the first treatment dose administration date. There is no day zero, hence the study day for patients who took at least one dose will be computed as follows:

Study Day = assessment date – treatment start date + 1,

if the assessment date is on or after the treatment date; or

Study Day = assessment date – treatment start date,

if the assessment date is earlier than the treatment date.

The end of this study is defined as the date when the last patient, last visit occurs. The end of the study is expected to occur approximately 6 months after the last study drug administration for the last patient has occurred. The total length of the study, from screening of the first patient to the end of the study, is expected to be approximately 1.5 years.

After completing study treatment in the current study, the patient will be eligible to enroll in an open label extension (OLE) study (BN40955) with active RO7234292 compound, provided the data from the ongoing RO7234292 program support continued development, the patient meets the inclusion and exclusion criteria for the OLE, and the OLE meets approval by the relevant competent authorities, IRBs, and ECs.

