4.7.3 Laboratory Data

Laboratory data including chemistry, hematology, CSF safety labs and urinalysis, will be collected throughout the study.

Summary statistics at each assessment time will be presented using the International System of Units (SI units; Système International d'Unités). Laboratory data not reported in SI units will be converted to SI units before processing.

Descriptive tables will be used to summarize absolute, change and percentage change from baseline by dose level and study day. Measurements reported as ' $>x$ ' or ' $<x$ ' will be handled as outlined in Section [4.5](#).

Spaghetti plots (with overlaid median) for absolute and change and percentage change from baseline values will be presented for all parameters by dose level on the numeric time scale.

In addition, the shifts (relative to the normal range) from baseline to the minimum and maximum post-baseline values will be presented. If a subject is missing a baseline value but had a post-baseline value, then the baseline assessment is labeled as "unknown". Likewise, if a subject had a baseline value but had no post-baseline values, then the minimum and maximum are labeled as "unknown". For each parameter, the incidence of shift to *low* (below the normal range) will be summarized using the minimum post-baseline values; the incidence of shift to *high* (above the normal range) will be summarized using the maximum post-baseline values.

Finally, the number of patients with abnormal absolute values for the CSF safety labs, according to the parameter ranges presented in [Table 1](#) will be summarized by dose level and visit and also as a listing. Red blood and white blood counts cannot be negative and the lower normal range limit is 0, hence no abnormal low values. Roche standard reference ranges, rather than the reference ranges of the Investigator will be used for all parameters.

For most parameters, the measured laboratory test result will be assessed directly using the Roche standard reference range. Certain laboratory parameters will be transformed to Roche's standard reference ranges. A transformation will be performed on certain laboratory tests that lack sufficiently common procedures and have a wide range of Investigator ranges, e.g., enzyme tests that include AST, ALT, alkaline phosphatase, and total bilirubin. Since the standard reference ranges for these parameters have a lower limit of zero, only the upper limits of the ranges will be used in transforming the data.

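### The scheduled-visits-only rule in SAP 4.7 is not lifted for the minimum/maximum shift tables, so off-schedule laboratory results can drop out of the worst-value summaries

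*SAP*

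**What the plan says.** The opening paragraph of SAP 4.7, which heads all the safety subsections, states: "Only scheduled visits will be presented in summary tables and both scheduled and unscheduled visits will be included in listings".

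SAP 4.7.3 adds that "the shifts (relative to the normal range) from baseline to the minimum and maximum post-baseline values will be presented". Incidence of shift to low uses the minimum; incidence of shift to high "will be summarized using the maximum post-baseline values". The section neither repeats the scheduled-only rule nor lifts it.

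Protocol 5.1.3.3 requires laboratory work that does not follow the visit schedule:

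- Results meeting a withholding criterion "must be repeated on new specimens as soon as possible, and results must be available prior to administering the next dose of study drug".
- Platelets at or below 100,000/mm³ are checked weekly. At or below 50,000/mm³ the instruction is "Monitor platelet counts daily until two successive values show improvement", then every 2 to 3 days, then at least weekly.
- ALT or AST above 3 × ULN: "Monitor weekly until ALT and AST return to" 1.2 × ULN or below.

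SAP 4.7.5 also summarizes the QTcF thresholds in its Table 4, without saying whether by visit or at any time. Protocol 4.5.7 allows unscheduled ECGs when clinically indicated. SAP section 2 gives the SAP precedence over the protocol.

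**The concern.** A shift to the minimum or maximum is meant to show each patient's worst result. If a programmer applies the general rule first and takes the extremes afterwards, the tests done because something looked wrong are removed before the worst value is found. The error has one direction: dropping values can only raise a minimum or lower a maximum, so shift incidence can stay the same or fall, never rise.

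The shift tables carry weight here. Protocol 6.4 plans the incidence of marked laboratory abnormalities, but the only abnormal-value counts described in SAP 4.7.3 are for CSF. For chemistry and haematology, the shift tables are therefore the main patient-level summary of worst values by dose level.

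**Working it through.** The plan gives no figure to reproduce. The check has four parts.

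**1. Does the exclusion follow from the text?** SAP 4.7 covers summary tables in general, and SAP 4.7.3 says shift incidence is summarized. No exemption is written, so the literal reading excludes unscheduled results. The phrase about minimum and maximum post-baseline values can also be read as meaning all values, so the text is open to two programs.

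**2. When does exclusion change the shift category?** The tables classify low, normal or high; they do not report depth. Illustrative platelet courses (×10³/mm³), with the lower limit of normal (LLN) assumed to be 150. That limit is inferred from the 125,000 to 150,000 exception in Protocol 4.1.2; the sponsor's standard range is not given.

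| Case | Scheduled values | Unscheduled values | Scheduled minimum | Overall minimum |
|---|---|---|---|---|
| A: a scheduled value is already low | 190, 95, 160 | 80, 60, 45, 120 | 95 (low) | 45 (low) |
| B: low only off schedule | 190, 170, 175 | 95, 45, 110 | 170 (not low) | 45 (low) |

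In A the category is unchanged; in B the shift is lost. Both results hold for any LLN above 95 and up to 170. The platelet monitoring trigger (100,000 or less) is out of range for any LLN above 100,000, and the ALT/AST trigger (above 3 × ULN) is out of range by definition. If a scheduled value pulled either trigger, the patient is already counted.

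Creatinine can differ. Reading the Protocol Table 1 criterion as a doubling from baseline, with baseline as a multiple of ULN:

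- 0.4 × 2 = 0.8, in range
- 0.5 × 2 = 1.0, in range
- 0.6 × 2 = 1.2, high

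A baseline of 0.5 × ULN or less can therefore meet the criterion with creatinine still normal. The same applies if eGFR or creatinine clearance falls below 60 while creatinine is normal. If the unscheduled repeat then exceeds ULN, a scheduled-only maximum misses the shift.

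**3. Is there room for off-schedule findings?** Nominal chemistry days after the first dose (Protocol Appendix 1) include 4, 28, 43, 71, 127 and follow-up, taken as Day 29 + 182 = 211. The gaps are:

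- 28 − 4 = 24 days
- 43 − 28 = 15 days
- 71 − 43 = 28 days
- 127 − 71 = 56 days
- 211 − 127 = 84 days

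**4. Size.** One missed patient changes incidence by 100/n percentage points:

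- n = 4 (planned per dose level): 25.0
- n = 12 (initial plan): 8.3
- n = 20 (maximum): 5.0

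These figures give the effect of one case, not its probability.

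**The case against.** The strongest reply is that the rule concerns which visits are presented, whereas a minimum/maximum shift table presents no visit, so the sponsor may already intend all values. That stands as a possible reading, and the defect is accordingly unclear wording with a harmful literal reading, not a proven exclusion.

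Other safeguards are real but partial. Unscheduled results stay in the listings, which are easy to inspect at 4 patients per level, but listings give no incidence by dose. Under Protocol 5.3.5.5, a laboratory result is an adverse event if it is symptomatic, changes treatment, leads to intervention or a change in concomitant therapy, or is judged clinically significant. Adverse events are summarized by severity, and those leading to interruption or discontinuation are listed separately. Platelets at 100,000/mm³ or ALT/AST just above 3 × ULN, however, prompt monitoring without necessarily changing treatment. With dosing only on Days 1 and 29, no dose remains to withhold during the 28-, 56- and 84-day gaps. The adverse event route is therefore a backstop, not a substitute.

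It is also fair that Protocol 5.1.2.3 and 5.1.2.5 report no clinically significant platelet reductions or liver enzyme elevations in clinical studies of this drug to date, so such cases may be rare.

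**Conclusion.** The point holds as a gap in the wording that can understate shift incidence. It requires the literal reading of SAP 4.7, plus a patient whose abnormality appears only off schedule or whose in-range scheduled value prompts an out-of-range repeat. One such patient is worth 25 points within a planned dose level. The platelet example assumes an LLN between the stated bounds; the creatinine example assumes the doubling reading.

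A reader might infer more than this, and the documents do not support it:

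- *That toxicity is understated in general, most of all in patients who stop drug.* Repeats after an out-of-range scheduled value do not change the category. Only the Day 29 dose can be withheld, safety laboratory tests are scheduled on Day 28, and early termination is itself a scheduled visit.
- *That dose decisions are biased.* Protocol 3.1 bases them on ongoing review of all available medical data, not on the shift tables.
- *That the CSF abnormality counts have the same fault.* SAP 4.7.3 defines them by visit, where a scheduled-only rule is ordinary.
- *That mandated ECG monitoring is lost.* Protocol Table 1 mandates no repeat ECGs, and SAP 4.7.5 lists all ECG data. The QTcF summaries are affected only if they count patients at any time post-baseline.

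**What to change.** Add to SAP 4.7 or 4.7.3: shift tables based on the minimum or maximum post-baseline value use all post-baseline results, scheduled and unscheduled. Say the same in SAP 4.7.5 for QTcF threshold summaries that count patients at any time post-baseline, and state there whether Table 4 is by visit or at any time. Keep the scheduled-only rule for by-visit descriptive tables, including the by-visit CSF abnormality counts.

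No new data are needed. The cost is a sentence or two and a change to a programming filter. The safety figures may look slightly less favourable.

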4.7.1 Exposure of Study Medication

Duration of treatment exposure (in days) to study drug will be calculated as:

$$\text{Date of last dose} - \text{Date of first dose} + 1$$

Summary tables for treatment exposure will be presented by dosing level. Number of doses received will also be reported.

4.7.2 Adverse Events

All treatment-emergent adverse events (TEAEs) and serious adverse events (SAEs) will be summarized for each dose level and for all patients using the Medical Dictionary for Regulatory Activities (MedDRA) coding by system organ class, preferred term, relationship to Study Drug, and severity. Missing data will be handled as described in Section 4.6. Percentages presented in AE tables will display the percentage of patients within a treatment dose level experiencing the AE at least once.

For frequency counts by preferred term, multiple occurrences of the same AE in an individual are counted only once. For overall total number of events, multiple occurrences of the same AE in an individual are counted separately.

An adverse event will be regarded as treatment emergent adverse event (TEAE) if the event occurs after the first dose of treatment or worsened after treatment.

Adverse events that occur before first dose administration and are not related to study procedure will be included in data listings only. SAEs and non-serious AEs that lead to treatment discontinuation or treatment interruption will be listed separately. Selected AEs, for instance procedure related AEs, will be summarized and listed separately.

Additional analyses will be considered to describe the impact of COVID-19 on patient safety.

4.7.3 Laboratory Data

Laboratory data including chemistry, hematology, CSF safety labs and urinalysis, will be collected throughout the study.

Summary statistics at each assessment time will be presented using the International System of Units (SI units; Système International d'Unités). Laboratory data not reported in SI units will be converted to SI units before processing.

Descriptive tables will be used to summarize absolute, change and percentage change from baseline by dose level and study day. Measurements reported as ' $>x$ ' or ' $<x$ ' will be handled as outlined in Section [4.5](#).

Spaghetti plots (with overlaid median) for absolute and change and percentage change from baseline values will be presented for all parameters by dose level on the numeric time scale.

In addition, the shifts (relative to the normal range) from baseline to the minimum and maximum post-baseline values will be presented. If a subject is missing a baseline value but had a post-baseline value, then the baseline assessment is labeled as "unknown". Likewise, if a subject had a baseline value but had no post-baseline values, then the minimum and maximum are labeled as "unknown". For each parameter, the incidence of shift to *low* (below the normal range) will be summarized using the minimum post-baseline values; the incidence of shift to *high* (above the normal range) will be summarized using the maximum post-baseline values.

Finally, the number of patients with abnormal absolute values for the CSF safety labs, according to the parameter ranges presented in [Table 1](#) will be summarized by dose level and visit and also as a listing. Red blood and white blood counts cannot be negative and the lower normal range limit is 0, hence no abnormal low values. Roche standard reference ranges, rather than the reference ranges of the Investigator will be used for all parameters.

For most parameters, the measured laboratory test result will be assessed directly using the Roche standard reference range. Certain laboratory parameters will be transformed to Roche's standard reference ranges. A transformation will be performed on certain laboratory tests that lack sufficiently common procedures and have a wide range of Investigator ranges, e.g., enzyme tests that include AST, ALT, alkaline phosphatase, and total bilirubin. Since the standard reference ranges for these parameters have a lower limit of zero, only the upper limits of the ranges will be used in transforming the data.

Standard and marked reference range for CSF laboratory parameters are presented in [Table 1](#), given that there were no internal standards for those parameters.. There is no difference in the standard and marked reference ranges for protein and Leukocytes except for Glucose and Erythrocytes upper limits.

Table 1. CSF Safety Labs Standard (Marked) Reference Ranges

Parameter	Standard Range			Marked Range
	Low	Normal	High	High
Glucose (mmol/L)	<2.2	2.2-3.9	>3.9	>4.4
Protein (g/L)	<0.15	0.15-0.5	>0.5	
Erythrocytes (cells/mm ³)		0	>0	>5
Leukocytes (cells/mm ³)		0-5	>5	

4.7.4 Vital Signs

Primary vital signs (pulse rate, systolic and diastolic blood pressure, temperature and respiratory rate; all supine after resting for approx. 5 minutes) and body weight will be measured at screening and protocol specified visits.

Absolute values and changes from baseline will be summarized with descriptive statistics by dose level and study day.

Spaghetti plots (with overlaid median) for absolute and change from baseline values will be presented for all parameters by dose level on the numeric time scale.

Listings of subjects meeting any of the abnormality criteria (according to Roche Standard ranges) outlined in [Table 2](#) will be provided.

Table 2. Vital Signs (Supine) Abnormality Ranges

Parameter	Low	Normal	High
Pulse rate (beats/min)	<60	60-100	>100
Systolic blood pressure (mmHg)	<90	90-130	>130
Diastolic blood pressure (mmHg)	<60	60-80	>80
Temperature (C)	<36.5	36.5-37.5	>37.5
Respiratory rate (breaths/min)	<8	8-20	>20

4.7.5 Electrocardiogram

A standard 12-lead electrocardiogram (ECG) will be recorded at study visits outlined in the protocol. ECG characteristics recorded include, HR, QRS duration, and PR and QT intervals. Changes in T-wave and U-wave morphology and overall ECG interpretation will also be documented on the eCRF. T-wave information will be captured as normal or abnormal. U-wave information will be captured in two categories: absent/normal or

abnormal. RR and QT corrected according to Frederica's (QTcF) formulas used at sites are defined as following:

- $RR = 60/HR$ and
- $QTcF = QT/RR^{1/3}$

The absolute values as well the changes from baseline will be summarized with descriptive statistics by dose level and study day. All ECG data will be listed.

In addition, abnormal findings for ECG parameters (according to [Table 3](#), Roche Standard ranges) will be listed. If a patient has an abnormal finding, all parameters will be reported. Abnormal absolute QTc and change in QTc interval, as presented in [Table 4](#) will also be summarized. Abnormal ECG Interpretation, U-wave and T-wave will also be listed.

Spaghetti plots (with overlaid median) for absolute and change from baseline values will be presented for all parameters by dose level on the numeric time scale.

Holter ECG recordings will also be recorded. Details on their collection and analysis will be detailed and provided in a separate document. In addition, details on QTc-concentration analysis will be detailed and provided in a separate document.

Table 3. ECG Parameters Abnormality Ranges

Parameter	Low	Normal	High
HR (beats/min)	<40	40-100	>100
PR Interval (msec)	<120	120-200	>200
RR Interval (msec)	<[contact]	>1500
QRS Duration (msec)	<40	40-120	>120
QT Interval (msec)	<200	200-500	>500
QTcF interval (ms)	<350	350-450	>450

Table 4. Criteria for abnormal absolute QTc and change in QTcF interval

Parameter	Criteria
QTcF interval (ms)	>450
	>480
	>500
QTcF change from baseline (ms)	>30
	>60

